Menstrual health is a significantly under-researched aspect of women's health, particularly among adolescents and young adults in low- and middle-income countries(1), even though menstrual disorders affect up to 75% of them and often interfere with daily functioning and overall well-being. (2). In Bangladesh, female university students frequently experience menstrual disorders such as dysmenorrhea, premenstrual syndrome (PMS), and menstrual irregularity (MI). These conditions are often aggravated by modifiable lifestyle factors including poor dietary intake, physical inactivity and food cravings for high fat and sweet food (3).

This study evaluated the effectiveness of a structured behavior change communication (BCC) intervention designed to improve menstrual health among female university students in Bangladesh. The intervention focused on three key menstrual health outcomes: dysmenorrhea, PMS, and MI. It promote a sustainable, non-pharmacological approach to managing common menstrual disorders through behavior and lifestyle changes including improved physical activity and dietary diversity.

The study employed a quasi-experimental design involved two groups: an intervention group that received BCC module and a control group that did not. Participants were female undergraduate students aged 19 to 25 years, residing in dormitories at three public universities in Bangladesh i.e. Patuakhali Science and Technology University (PSTU), Barishal University (BU), and Khulna University (KU). Ethical approval was obtained from the Shahjalal University of Science and Technology Research Ethics Board (Ref. No. AST/002/258), and all participants provided written informed consent. The BCC intervention comprised three interactive educational sessions

delivered between May 20 and June 30, 2023, by trained female facilitators. The first session addressed menstrual disorders and associated risk factors, the second focused on healthy dietary practices, and the third emphasized physical activity (including yoga) and other relevant lifestyle modifications. To reinforce the content, follow-up visits were conducted every two months over a six-month period. Post-intervention data collection was carried out between February and March 2024.

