The treatment variable was exposure to the BCC intervention (yes/no). The covariates included physical activity, obesity, dietary habits, lifestyle factors, and socio-demographic characteristics. Physical activity was classified according to WHO guidelines (7) as: (i) sedentary: light-intensity activities; (ii) active: moderate-intensity activities for 150–300 minutes per week; and (iii) athlete: vigorous-intensity activities for 75–150 minutes per week. Obesity was assessed using body mass index (BMI, kg/m²) and categorized according to WHO Asian-specific cut-offs (8): (i) underweight (<18.5), (ii) normal weight (18.5–22.9), (iii) overweight (23.0–27.5), and (iv) obese (>27.5). Dietary information was collected using a five-day 24-hour recall method, and dietary diversity score (DDS) was calculated following FAO guidelines (9) . Lifestyle-related covariates included food cravings for high-fat or sweet foods (10), skipping breakfast, sleep duration, bedtime and caffeine intake (11). Socio-demographic variables included family history of menstrual disorders, age at menarche, marital status, and participants' residence as well as parental educational and occupational status.

Data were collected through interviewer-administered, culturally adapted, and validated Bengali-questionnaires. Descriptive statistics summarized baseline characteristics. Group differences were tested using chi-square and t-tests. Propensity scores were estimated using logistic regression, and covariate balance post-matching was evaluated using standardized mean differences (SMD <10%). Intervention effects were analyzed using conditional logistic regression on the matched sample, and logistic regression (bivariate/multivariate) on the unmatched sample. Sensitivity analyses included covariate balance diagnostics, estimation of average treatment effects (ATE/ATT), and Bayesian logistic regression with log Bayes factor.

This study complies with U.S. regulatory requirements for clinical trial registration and reporting under 42 CFR Part 11. The responsible party confirms that all submitted information is complete and accurate, and that the study protocol, statistical analysis plan (SAP), and informed consent form (ICF) reflect the approved trial objectives and design.

Participant flow

Recruitment details

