Outcome	Group	Overall number of baseline participants	Baseline analysis population description
Dysmenorrhea	Intervention	234	After recruitment and data quality checks, 234 participants were included in the initial analysis. After propensity score matching, 98 were retained.
	Control	238	From 238 eligible controls, 98 matched participants were used in the final matched analysis.
	Total	472	The final matched sample included 196 participants (98 per group), selected through 1:1 propensity score matching without replacement using a caliper of 0.01.
PMS and MI	Intervention	228	228 participants provided valid and complete responses and were included in the baseline analysis. After matching, 98 were included in the final matched analysis.
	Control	228	228 participants were eligible for baseline analysis. After matching, 98 were used for final analysis.
	Total	456	A total of 196 participants (98 in each group) were retained after 1:1 matching with a 0.01 caliper and no replacement.

Baseline Measure Information

The baseline characteristics of study participants were assessed using a combination of study-specific and standard measures to comprehensively capture their lifestyle, nutritional, reproductive, and socio-demographic profiles (Table 6). Study-specific measures included

physical activity level (categorized according to WHO guidelines), body mass index (BMI) using Asian-specific cut-offs, and minimum dietary diversity (MDD) based on a 5-day food diary aligned with FAO recommendations. Additional lifestyle factors assessed included food cravings, skipping breakfast, sleep duration, caffeine intake frequency, and bedtime. Reproductive health and demographic factors such as age, age at menarche, marital status, and participant's residence, family history of menstrual disorders, as well as parental education and occupation were also recorded. These baseline measures were used to describe the participant population and to adjust for potential confounding in subsequent analyses.

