Dietary diversity Score (DDS)	MDD (scoring ≥ 5)	Dietary diversity was assessed using a 5-day food diary based on the 24-hour recall method, following FAO guidelines. Food items were classified into 10 predefined groups, and scores ranged from 0 to 10. Minimum dietary diversity (MDD) was defined as achieving a score of 5 or more.	Count of participants	Not applicable	Yes / No	Participants
Food Craving	Food craving for high-fat and sweet food	Self-reported craving for high-fat and sweet food.	Count of participants	Not applicable	Yes / No	Participants
Skipping breakfast	Skipping breakfast	Reported skipping breakfast one or more times during the last week.	Count of participants	Not applicable	Yes / No	Participants
Sleep duration	Sleep hours per night	Based on self-reported average nightly sleep duration	Count of participants	Not applicable	<7 hrs / ≥7 hrs	Participants
Caffeine consumption	Frequency of caffeine Intake	Based on frequency of caffeine intake per week; categorized as infrequent (<3 times/week) or frequent (≥3 times/week)	Count of participants	Not applicable	Infrequent / Frequent	Participants

Bedtime	Bedtime (hours)	Bedtime was classified into two groups: ≤23:00 hours and >23:00 hours, based on a 24-hour clock format	Count of participants	Not applicable	Before or at 23:00 / After 23:00	Participants
Family history of menstrual disorders	Family history of menstrual disorders	Participants reported whether they had family history of any kind of menstrual disorders viz. dysmenorrhea, PMS, or IMC.	Count of participants	Not applicable	Yes / No	Participants
Age (Not study-specific measure)	Age	Treated as continuous variable	Mean	Standard deviation	Not applicable	Participants
Menarche age	Age at menarche	Reported age at first menstruation in years and treated as continuous variable.	Mean	Standard deviation	Not applicable	Participants
Marital status	Marital status	Marital status was self-reported. Participants categorized as divorced, separated, or recently married were grouped under ever married. All others were classified as never married.	Count of participants	Not applicable	Never married / Ever married	Years
Residence	Participant's residence	Living arrangement of the participants during the study time.	Count of participants	Not applicable	With Family / at student dormitory	Participants

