Father's Education	Father's educational status	Education levels were categorized as: "Below secondary education" (no formal education, primary, or incomplete secondary schooling) and "Secondary or higher education" (completed secondary school, higher secondary, college, or university)	Count of participants	Not applicable	Below Secondary (0-5 y schooling) / Secondary and above(> 5 y schooling)	Participants
Mother's Education	Mother's educational status					
Father's Occupation	Father's occupational status	Occupational status was self-reported as either Formal (salaried or secure jobs) or Informal (homemaking, daily wage, or insecure work)	Count of participants	Not applicable	Formal / Informal	Participants
Mother's Occupation	Mother's occupational status					

Number of baseline participants

The number of baseline participants is the same as the overall number of baseline participants, as it includes all individuals who completed baseline data collection and met the data quality criteria.

Although PSM was later used to create comparable groups for outcome analysis, the baseline measures reflect the entire recruited sample before matching. Therefore, no separate or reduced sample size is reported in this section.

Baseline Measure Data

Baseline characteristics were assessed at the time of outcome evaluation for both the intervention and control groups. Although data were collected post-intervention, propensity score matching was applied to balance pre-existing covariates and reduce selection bias in estimating the treatment effect. The Table 7(A and B) present the baseline values for each measure across the intervention and control groups, as well as for the total study population.

Table 7A. Comparison of baseline characteristics between study groups for dysmenorrhea outcome

Variables	Control (n = 238)	Intervention (n = 234)	Total (N = 472)
Physical activity level			
Sedentary	206 (43.6)	114 (24.2)	320 (67.8)
Active and Athlete	32 (6.6)	120 (25.6)	152 (32.2)
BMI (kg/m²)			
Normal weight (18.5-22.9)	83 (17.6)	171 (36.2)	254 (53.8)
Underweight (<18.5)	44 (9.3)	37 (7.8)	81 (17.2)
Overweight and obese (>22.9)	111 (23.5)	26 (5.5)	137 (29.0)
MDD (scoring ≥ 5)			
No	153 (32.4)	96 (20.3)	249 (52.8)
Yes	85 (18.01)	138 (29.2)	223 (47.2)
Food craving for high fat and sweet food			
No	77 (16.3)	164 (34.8)	241 (51.1)

Yes	161 (34.1)	70 (14.8)	231 (48.9)
Skipping breakfast			
No	72 (15.5)	169 (35.8)	241 (51.1)

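### Lifestyle covariates and BMI used in the primary matching were measured after the intervention but are treated as baseline, so the adjusted estimates may not equal the total effect of BCC

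*Combined protocol and SAP*

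**What the plan says.** **Timing.** Under Baseline Measure Data: "Baseline characteristics were assessed at the time of outcome evaluation for both the intervention and control groups". The next sentence reads: "Although data were collected post-intervention, propensity score matching was applied to balance pre-existing covariates". Just above, under Number of baseline participants, the count is justified because "it includes all individuals who completed baseline data collection and met the data quality criteria".

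**Content of the intervention.** Under Detailed description of the study, the first session covered menstrual disorders and their risk factors, "the second focused on healthy dietary practices, and the third emphasized physical activity (including yoga) and other relevant lifestyle modifications". The same section says that the approach works "through behavior and lifestyle changes including improved physical activity and dietary diversity".

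**Use of the covariates.** Baseline Measure Information says: "These baseline measures were used to describe the participant population and to adjust for potential confounding in subsequent analyses". It then lists 13 matching covariates for dysmenorrhea and eight for PMS and MI. The 13 also enter the regression models and the average treatment effect, overall (ATE) and on the treated (ATT). The eight are also adjusted for in estimating the treatment effects.

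**Status of the analyses.** The SAP (Statistical analysis overview) makes conditional logistic regression on the matched sample the primary analysis. Item 3 of Other statistical analysis presents ATE and ATT as supporting the stability of the effect.

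**Limitations.** Limitation and caveats mentions the lack of randomization, residual confounding, missed sessions, control group characteristics that were not assessed, and dietary recall. It does not mention adjustment for variables that the intervention may have changed.

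**The concern.** Matching removes confounding when the covariates were fixed before exposure. If a covariate was measured afterwards and the intervention moved it, matching compares women who ended up alike on something the intervention may have altered. That can take out part of the effect, or distort it in another way if the covariate and the outcome share an unmeasured cause. Here the covariates include the two behaviours through which the module is said to work.

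Table 11 presents its odds ratios as the impact of the BCC module. A reader who is told that the covariates were baseline and pre-existing would take the matched odds ratio for the whole effect of offering the module, adjusted only for prior differences. The documents do not establish that. ATE and ATT rest on the same covariates, so their agreement with the odds ratio cannot reveal the problem.

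**Working it through.** **1. Order in time.** Sessions ran from 20 May to 30 June 2023 and follow-up from 15 July 2023 to 15 January 2024. Outcomes and covariates were collected in February to March 2024. The three study periods (implementation, follow-up, post-intervention evaluation) include no pre-intervention data collection. Table 6 shows how recent one item is: "Reported skipping breakfast one or more times during the last week". With data collected in February to March 2024, that week falls after the last support visit. The text about completed baseline data collection therefore matches nothing else in the document.

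**2. Which matching covariates BCC may have changed** (lists from Baseline Measure Information)

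| Covariate | Dysmenorrhea | PMS and MI | Link to BCC |
|---|---|---|---|
| Physical activity | yes | yes | named route |
| Dietary diversity | yes | yes | named route |
| BMI | yes | yes | by inference |
| Food craving | yes | yes | by inference |
| Breakfast skipping | yes | yes | by inference |
| Sleep duration | yes | yes | by inference |
| Caffeine | yes | no | by inference |
| Total | 7 of 13 | 6 of 8 | |

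**3. Reproducing the crude odds ratios** (Table 10 counts against Table 11)

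- Dysmenorrhea: (75 × 29)/(159 × 209) = 0.066, 95% CI 0.041 to 0.105. Printed: 0.07 (0.04, 0.11). Agrees.
- PMS: (23 × 83)/(205 × 145) = 0.064, 95% CI 0.039 to 0.107. Printed: 0.07 (0.04, 0.11). The interval agrees; the point estimate would round to 0.06.
- MI: the row is inconsistent as it reads, since the two control cells add to 118 + 205 = 323 against 228 controls. Taking 228 − 118 = 110 irregular controls and 228 − 23 = 205 regular intervention women gives (23 × 118)/(205 × 110) = 0.12, 95% CI 0.073 to 0.199. Printed: 0.12 (0.07, 0.20). It also gives (110 + 23)/456 = 29.2%, as printed. This reading is an assumption.

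**4. Group differences at outcome evaluation** (Table 7A, absolute values). The table's percentages use the total of 472, so within-group proportions were recomputed. SMD = (p1 − p0)/√{[p1(1 − p1) + p0(1 − p0)]/2}.

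| Variable | Intervention | Control | SMD |
|---|---|---|---|
| Active or athlete | 120/234 = 51.3% | 32/238 = 13.4% | 0.88 |
| Overweight or obese | 26/234 = 11.1% | 111/238 = 46.6% | 0.85 |
| Minimum dietary diversity met | 138/234 = 59.0% | 85/238 = 35.7% | 0.48 |
| Food craving | 70/234 = 29.9% | 161/238 = 67.6% | 0.82 |
| Breakfast skipping | 65/234 = 27.8% | 166/238 = 69.7% | 0.93 |
| Sleep under 7 hours | 79/234 = 33.8% | 163/238 = 68.5% | 0.74 |
| Frequent caffeine | 77/234 = 32.9% | 173/238 = 72.7% | 0.87 |
| Family history | 37/234 = 15.8% | 78/238 = 32.8% | 0.40 |

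Age at menarche: (13.4 − 12.1)/√[(1.7² + 1.5²)/2] = 0.81. The last two traits cannot be effects of BCC, yet they differ as well.

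**5. Crude risk differences beside Table 12**

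| Outcome | Crude difference | ATE | ATT |
|---|---|---|---|
| Dysmenorrhea | 75/234 − 209/238 = −0.56 | −0.23 | −0.27 |
| PMS | 23/228 − 145/228 = −0.54 | −0.39 | −0.42 |
| MI (110 irregular controls) | 23/228 − 110/228 = −0.38 | −0.30 | −0.31 |

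**6. What this shows.** Steps 1 and 2 carry the point. Steps 4 and 5 are context. The gaps in step 5 mix confounding removed, mediation possibly removed, and a change of population. Without pre-intervention values they cannot be split.

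**The case against.** The strongest reply is that adjustment may be right. Groups were formed by voluntary registration and attendance, and women who register may already have been more active and eaten better. The differences in age at menarche and family history show that the groups differed in ways BCC could not cause. If the lifestyle gaps predate the sessions, leaving these variables out would leave confounding in. This stands, and it is why no direction of bias is claimed. It does not rescue the label: calling the variables pre-existing asserts one of two explanations that the data cannot tell apart.

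A second reply is disclosure. Baseline Measure Data states the timing openly, Table 11 prints the crude odds ratio beside the adjusted ones, and the limitations concede residual confounding and limited causal inference. This also stands in part. What is missing is the consequence. Residual confounding means too little adjustment; adjusting for possible mediators is a different problem.

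A reader might go further and infer that the fall from −0.56 to −0.23 for dysmenorrhea is the share of the effect that matching removed, or that the crude figure is the true effect. The documents support neither. The crude figure is confounded by self-selection. Matching also dropped 136 of 234 (58%) intervention women for dysmenorrhea and 130 of 228 (57%) for PMS and MI.

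**Conclusion.** The concern holds in a limited form. By the protocol's own account, the covariates labelled baseline were measured after the intervention. Seven of 13 and six of eight of the matching covariates are ones BCC may have changed, two of them by its stated mechanism. The primary matched odds ratio, the multivariable odds ratio, ATE and ATT therefore may not equal the total effect of BCC, and the limitations do not say so.

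The direction and size of any bias are unknown, and no corrected estimate can be computed from the documents. The conclusion does not depend on how the MI row of Table 10 is read. It assumes that the statement of timing under Baseline Measure Data is correct and that no undescribed pre-intervention data exist. For BMI, craving, breakfast, sleep and caffeine, it also rests on inference about what the sessions could change. It does not follow that the adjustment was wrong or that BCC had no effect.

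**What to change.** 1. **Labels.** Stop calling the lifestyle variables and BMI baseline or pre-existing, and state that they were measured post-intervention. Places: Baseline Measure Information; Number of baseline participants; Baseline Measure Data; the Group descriptions under Outcome measures and Adverse event information; and, in the SAP, Statistical analysis overview and item 1 of Other statistical analysis. Reconcile this with the text about completed baseline data collection.
2. **Meaning of the estimates.** With Tables 11 and 12, describe the matched and multivariable odds ratios, ATE and ATT as adjusted for lifestyle variables measured after the intervention, which may not equal the total effect of BCC. Qualify item 3 of Other statistical analysis: ATE and ATT use the same covariates, so their agreement does not test this problem.
3. **Limitations.** Add that possible mediators were adjusted for and that no pre-intervention lifestyle or outcome measurement is described, so mediation and self-selection cannot be separated.
4. **Sensitivity analysis.** Post hoc, refit the matching for each outcome using only traits BCC is unlikely to change: age, age at menarche, family history, marital status, and parental education and occupation. Run it with and without residence, which was recorded as of the study period. Report balance and number matched beside the current analysis, and claim the result as neither the causal effect nor a bound.

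Items 1 to 3 are wording changes. Item 4 needs an additional matching and regression for each outcome, with the residence variant, on data already held. The price is a weaker causal claim. The refit also leaves any prior lifestyle differences unadjusted, and the report must say so.
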